- **Adherence** (to medication) - Following a medicine regimen according to the recommended dosage and frequency.
- **Android** - A free and open-source smartphone operating system created by Google.
- **App** - An application created for a smartphone. An app can be made for Android, iPhone (iOS), BlackBerry or Windows Phone.
- **CD4** - Also known as CD4+ T helper cells, which are an essential part of the human immune system. The number of CD4 cells found per cubic millimetre determines if an HIV-positive individual should be on ARV medication.
- **Linkage (to care)** - Attendance to follow-up HIV care by an HIV-positive patient. In the current study linkage to care is defined as attendance to a follow up clinical visit and laboratory test within 6 months of HIV diagnosis.
- **mHealth** - The use of mobile devices to support health care.
- **Retention (in care)** - Attending to regular follow-up medical visits once receiving HIV care. In the current study, retention in care is defined as continuation of HIV care (regular clinic visits with laboratory tests and/or medicine pickup) after the linkage to care visit.
- **Smartphone** - A mobile phone that runs an operating system that allows the installation of apps. Most phones that cost \$50 USD or more are smartphones as are all Android, Apple, and Windows Phone devices.

Rationale & background

South African HIV testing rates are high, with almost 50% of adults knowing their status (Shisana et al, 2014). However, immediate linkage to the next levels of care of newly diagnosed HIV-positive individuals is very low throughout the region (Rosen, 2011). Improved access to point of care CD4 counts, widely anticipated to have improved linkage to care, have yielded disappointingly limited success, suggesting other interventions are required (Larson, 2013; Faal, 2011). Linkage to care and adherence to medication is higher in HIV than in most other chronic illnesses, and this is widely ascribed to widespread HIV patient education programmes within communities; further patient empowerment and involvement in care may additionally improve retention. Current demographic data on those specifically accessing antiretroviral (ART) care, however, suggests that younger people and men are disproportionately less likely to make this link (Takuva et al 2015), again suggesting that these two groups would benefit from more focus.

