While designing the study, the team was conscious of the limited resources of the potential participants. The app will be installed by the research team using a USB connection, negating the need of data charges to download/install it. Additionally, all of the app's background HIV information and computational logic will be built-in, meaning that any new CD4 count/viral load result sent to the app will only be a few kilobytes each, including the data used for logging into the app. This translates to a maximum cost of R0.02 (or \$0.0017 USD) on Vodacom's out-of-bundle data rates (which is currently the most expensive data option, out-of-bundle or in-contract, in South Africa¹) per laboratory result received. Another option for the study was a secure website which works similarly to the app. Such a website would increase data costs for the patient (since everything on the site would have to be downloaded each time it was visited) and would not allow for notifications. For these reasons, a smartphone app was chosen for the study.

¹ For details of Vodacom's out-of-bundle (read: most expensive) data pricing, please see: <http://www.vodacom.co.za/vodacom/shopping/data/prepaid-data>

Study goals & objectives

Study goal

To determine if a smartphone app that provides laboratory results (CD4 count and viral load) and health information relating to HIV to patients is acceptable to individuals who are newly diagnosed with HIV (will they use it?), increases linkage to and retention in care (do they attend follow up visits at a higher rate?) and can be feasibly implemented in a clinical setting.

Primary objective

To test whether linkage to HIV care is improved by providing clients with access to a smartphone-enabled application (app) when compared to standard of care around 6 months post-diagnosis.

Secondary objectives

1. To compare ART initiation rates between intervention and control arms.
2. To assess the feasibility and acceptability of receiving laboratory results to a personal smartphone.
3. To assess secondary effects from improved patient information, including return rates after falling out of care (assessed through routine patient record reviews), patient satisfaction (through face-to-face surveys at the 6-month follow-up visit and end of the study), and rates of additional blood tests (especially CD4 count, viral load).
4. To assess patient knowledge levels of their laboratory results.

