Patients randomised to the intervention arm will be assisted with downloading and installing the app, and setting up their accounts with a username, password and PIN. How to use the app including accessing laboratory data and HIV support information will also be explained. All patients will be recruited at first CD4 count test as the classification into 'wellness' or 'treatment' will not occur until their return to the clinic. As standard of care, both wellness and treatment patients are requested to return after 6 months for a follow-up phlebotomy and CD4 count (for wellness patients) or viral load (for patients on ART) testing. All study

participants will be assumed to be linked to care if they attend for the follow up laboratory tests by the end of the 8th month after joining the study. The study team is aware that some patients will need ART bloods at 3 months, and some will need a follow-up VL due to not being suppressed at 6 months. With this in mind, the app will notify the study participant to go for an appointment 6 and 12 months after recruitment irrespective of their initial CD4 count (both wellness and treatment groups). To provide additional support to study participants in the treatment arm, the app will monitor the first viral load result and notify participants with a viral load of >1000 copies/mm³ to go to the clinic in two months, while notifying participants with a viral load of <1000 copies/mm³ to go to the clinic after six months. This logic will be built into the app and is per current South African HIV Guidelines published 24 December 2014 by the National Department of Health.

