The aim of the study is to show that smartphone apps work for that proportion of the population that currently have Android smartphones, not that it works for the general population. Smartphone purchase is rapidly increasing in South Africa, with 75% of new cell phones sold in South Africa currently being smart phones. We expect that randomization and a large sample size will enable us to have a reasonable balance between the arms, unless participants randomized to the control group request study withdrawal due to not getting the app.

Sample Size

Based on a primary endpoint of a second HIV-linked laboratory test (CD4, viral load) being performed at a clinical facility, within 8 months after the HIV-positive result, suggesting successful attendance and entry into HIV care, we anticipate at least 1000 patients in each arm will be needed. The study team expects to see a 20% difference in linkage to care levels through the app (using a second HIV-linked laboratory test as an indicator for linkage to care). The sample size is calculated based on 80% power, 0.05 significance with a loss-to-follow-up rate of approximately 27% (Hillbrow CHC data). Both ART and pre-ART patients will be expected to return for a follow-up laboratory test around 6 months after diagnosis; ART patients for a viral load, and pre-ART for a follow-up CD4 count.

In South Africa, both younger and male clients have lower linkage to care rates than females and individuals over 25. In order to conduct subgroup analysis on these higher-risk populations (young people and men), there will be an over-sampling of male patients and those between the ages of 18 (the age of majority) and 25 for both the intervention and control arms given that it has been shown that these groups are less likely to access health services efficiently (Kranzer, 2010). These populations will be recruited until 250 of these individuals are included in both arms to ensure the study is powered to analyse the effect in these key subgroups. Based on a 20% difference in linkage to care for the intervention/app arm with an 80% power, a significance level of 0.05 and a loss-to-follow-up rate of 40% a sample size of 97 per arm is required. Again, the study team will over-sample based on the proof-of-concept nature of the study.

Figure 2: *Recruitment flow chart*

App specifications

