The app will measure the number of times and dates/times that it is opened, relative to the sending of the push notifications, so as to understand usage. In addition, we will be able to tell if the app is opened during a clinic visit (as measured by a laboratory request), marking a possible showing of the result to a health care worker. Health care workers in the study sites will be briefed about and explained how the app works. Patients will be encouraged to use the call back facility if they have linked to care but are still receiving reminder notifications to do so; this should allow us to evaluate the accuracy of the single patient identifier use. Note that patients who have been linked to care at the study sites will automatically stop receiving the reminder notifications until the next time they are required to attend the clinic. An overview of app specifications can be seen below (Appendix III).

Prior to study recruitment, the study team will conduct at least two focus group discussions (FGD's) with potential study participants. These FGD's will test the ease of installation and use of the app, language level of the content, understanding of the laboratory test results, and satisfaction of the participants. Feedback from the FGD participants will be shared with the app developers who will make improvements to the app.

Patient follow-up

Patients will be followed up for a minimum of one year and maximum of 18 months to monitoring linkage to care and retention in care. We anticipate recruitment taking 3 months resulting in data spanning 15-18 months, over the 2 year lifetime of the project (if funding is secured, as per issues cited in the "Risks" section, below). The outcome of the primary objective (linkage to care) will be analysed 8 months after recruitment of the last participant to allow for patients link to care slightly delayed.

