The primary outcome, linkage to care around 6 months after initial diagnosis, will be available after the final patient recruited has reached the 8 month mark, allowing immediate assessment of the feasibility and immediate impact of the app on initial linkage to care. Thereafter, retention in care, defined as continuation of HIV care (regular clinic visits with laboratory tests and/or medicine pickup) after the linkage to care visit will be assessed 12 months after linkage to care had been made.

Analysis will be done by the study team using STATA. Intention-to-treat will be the primary approach of the analysis and all missing data points will be considered to be loss-to-follow-up. Analysis of the primary outcome will be based on a chi-squared test comparing the proportion of individuals between the study arms and within study sites. A

logistic regression model, with linkage to care as the dependent variable, will be a secondary analysis of the primary outcome.

For secondary outcomes, chi-squared tests will be used for binary variables, Mann-Whitney-U tests for non-normally distributed variables, and t-tests for continuous variables. Relative risk calculations (at 95% confidence) will be used to compute binary variables. Survival analysis will be conducted to determine linkage outcomes at 6 months. A sensitivity analysis will be conducted using regression analysis to identify and adjust for potential confounders.

For the cost-effectiveness analysis, we will have data on direct costs and understand the resource requirements for the development of the app. We will corroborate our existing estimates of the smartphone data costs of the patient. The study team will collect data on clients' opportunity cost as part of the end of the study participant interview as linkage to care (as opposed to non-linkage to care) actually takes more time. We will use primary data collect through this study to calculate unit costs associated to providing HIV services.

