Study results will be presented at national and international HIV/AIDS management and clinician conferences and meetings. Study manuscripts will be submitted to the appropriate journals. Results outcomes will be shared at internal and external research days as well as academic meetings. All these dissemination activities will be planned and carried out in close collaboration with the World Bank team.

Duration

Planning is currently ongoing. Recruitment is expected to start: June 1 2015 with 8 months of follow up minimum. Should additional funding be found, a further 12 months of follow-up will be conducted (ending December 2016).

A brief overview is as follows:

Activity	Year 1												Year 2 (to be fully funded)											
	1	2	3	4	5	6	7	8	9	10	11	12	1	2	3	4	5	6	7	8	9	10	11	12
Project launch	█																							
Ethics application		█	█																					
Hiring		█																						
Training		█	█																					
Educational development		█	█	█																				
Smartphone app development		█	█	█	█																			
Patient recruitment						█	█	█																
Data analysis (6 month outcomes at 8 months)															█									
Participant follow-up																		█	█	█				
Data analysis (12 month outcomes at 14th month)																					█			
Report/article writing												█	█								█	█	█	█

Problems anticipated

Potential risks

The largest potential risk revolves around permission from tiers of government for the project to continue. We hope to perform this in different provinces, but are constrained by the limited funding times, so we will need to assess the quickest way forward after we have submitted for permission.

We have noted that funding is not currently committed for year two, and will mobilise internal and other funding should World Bank not be able to commit resources to completing the last phase. A 12 month extension is essential as the primary outcome extends into the second year. The second year will allow the team to look at the effects of the app on ongoing pre-ART monitoring and on patient information concerning VL testing, VL as an adherence tool, and actual viral suppression.

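### Retention is timed 12 months after linkage, which needs 18 to 20 months for linkage at months 6 to 8; the follow-up statements do not reliably supply this, and no denominator is given

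*Protocol*

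**What the plan says.** The Protocol's Analysis plan defines retention as "continuation of HIV care (regular clinic visits with laboratory tests and/or medicine pickup) after the linkage to care visit" and says that it "will be assessed 12 months after linkage to care had been made". The Study goal includes whether the app "increases linkage to and retention in care".

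Linkage has two windows. The Intervention section counts participants as linked if they "attend for the follow up laboratory tests by the end of the 8th month after joining the study". The definitions at the front of the Protocol say "attendance to a follow up clinical visit and laboratory test within 6 months of HIV diagnosis". On expected timing, the Sample Size section states: "Both ART and pre-ART patients will be expected to return for a follow-up laboratory test around 6 months after diagnosis".

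Several statements bear on how long people are followed:
- **Protocol, Patient follow-up:** "Patients will be followed up for a minimum of one year and maximum of 18 months", with three months of recruitment and data covering 15 to 18 months. The same section places a funding-dependent telephone contact at 12 months from recruitment. The activity chart under Duration puts the analysis of 12-month outcomes in a 14th month.
- **Protocol, Duration and Timeline:** recruitment from 1 June to 31 August 2015, at least 8 months of follow-up and, if money is found, "a further 12 months of follow-up will be conducted (ending December 2016".
- **SAP section 5:** recruitment over about 8 months.

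The Analysis plan makes intention-to-treat the primary approach and treats every missing data point as loss to follow-up. No section gives the denominator for retention. Retention is not among the objectives, outcomes or results table of the SAP (sections 3.2, 3.4, 3.5, 7.4).

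**The concern.** The retention clock starts at linkage, not at randomisation. This raises two problems.

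The first is time. Someone who links late needs a long total follow-up, and the Protocol's statements about its length do not agree with each other or with this requirement. Under the missing-data rule, a linker whose 12 months run past data closure could be scored as not retained, so that a calendar shortfall is reported as a failure of care.

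The second is the comparison. A participant who never links has no linkage date, so the outcome is undefined for that person. If retention is compared among linkers only, the groups are selected by an event after randomisation that the app is designed to change.

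At stake is the retention half of the study goal. The SAP says nothing that would settle either question.

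**Working it through.** **1. The Protocol's own span.** A maximum of 18 months less 3 months of staggered entry, with one closing date, gives 15 to 18 months. This reproduces the stated data span. The one-year minimum in the same section fits only as a lower bound.

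**2. Follow-up needed.** Required months = linkage month + 12.
- Linked at month 8: 8 + 12 = 20.
- Linked at month 6 (the expected time, and the limit in the definitions): 6 + 12 = 18.
- Linked at month 3 (the Intervention section notes that some patients have bloods then): 3 + 12 = 15.

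**3. Follow-up available under the Duration section.** From 1 June 2015 to 31 December 2016 is 19.0 months; from 31 August 2015 it is 16.0. The 20-month point falls between 1 February and 30 April 2017, so a month-8 linker is short by 20 − 19 = 1 to 20 − 16 = 4 months. If recruitment from 1 June 2015 takes the SAP's 8 months and the end date stays, the last entrant has 19 − 8 = 11 months.

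**4. Share of linkers with a full 12 months after linkage.** Assume that follow-up is spread evenly from a to b months. For linkage at month L the share is (b − (L + 12)) / (b − a), held between 0 and 1. For example, with 16 to 19 months and L = 6: (19 − 18)/(19 − 16) = 33%. For linkage spread evenly over months 0 to 8, average max(0, follow-up − 12)/8. With 15 to 18 months this is 4.5/8 = 56%, and with 16 to 19 it is 5.5/8 = 69%. All linkage times here are assumed.

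| Follow-up (months) | Basis | Month 3 | Month 6 | Month 8 | Even, 5.5 to 8 | Even, 0 to 8 |
|---|---|---|---|---|---|---|
| 12–18 | Patient follow-up, per patient | 50% | 0% | 0% | 1% | 37.5% |
| 15–18 | Patient follow-up, data span | 100% | 0% | 0% | 2% | 56% |
| 16–19 | December 2016 end, 3-month recruitment | 100% | 33% | 0% | 15% | 69% |
| 11–19 | December 2016 end, 8-month recruitment | 50% | 12.5% | 0% | 6% | 38% |
| 20 | Nominal 8 + 12 for everyone | 100% | 100% | 100% | 100% | 100% |

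**5. Effect of the missing-data rule.** Illustration: linkage at month 6, 16 to 19 months of follow-up, true retention of 80% (assumed). If cut-off windows are scored as not retained, observed retention is 0.333 × 80% = 27%.

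**6. Linkers-only comparison.** Inputs: control linkage 50% (the Protocol's Population section gives 50–55%) and app linkage 70% (the expected 20% difference, read as percentage points). Assume that 80% of those who would link anyway are retained, with no app effect on retention itself. Let r be the assumed retention in people who link only because of the app. Retention among app-arm linkers = (0.50 × 0.80 + 0.20 × r)/0.70, against 80% in control linkers. Over all randomised, with non-linkers counted as not retained, the arms have 0.40 + 0.20 × r and 0.40.

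| r | Linkers only, app minus control | All randomised, app minus control |
|---|---|---|
| 50% | −8.6 points | +10 points |
| 60% | −5.7 | +12 |
| 80% | 0 | +16 |
| 90% | +2.9 | +18 |

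The linkers-only difference changes sign with r, which the documents do not give. The all-randomised difference here comes wholly from extra linkage.

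**The case against.** The strongest reply has four parts.

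- **The Duration section offers 20 months.** Eight months plus a further 12 is exactly what a month-8 linker needs. That is correct as a sum. But the extension depends on funding not yet secured, and its own end date stops 1 to 4 months short. The fault is therefore a set of statements that disagree, not simply 20 months against 18.
- **Not everyone links at months 6 to 8.** A reader might infer that retention is mostly unmeasurable. The documents do not support this in general: linkage is scored on a qualifying test at any time up to month 8, and with linkage spread evenly over months 0 to 8 some 56–69% could be assessed with 15 to 19 months of data. The inference holds only if linkage clusters around month 6, as the Protocol expects, or if follow-up is as short as the per-patient minimum or the SAP's recruitment period implies.
- **Intention-to-treat is stated.** A reader might infer that the comparison is biased. No denominator is given, and the intention-to-treat sentence is compatible with using all randomised. What stands is that this sentence supplies no time point for people who never linked, and the definition itself refers only to care after linkage. The selection effect is a risk, not a demonstrated bias, and it is zero if the extra linkers are retained like the others.
- **The consequence is limited.** Retention is in the study goal but is neither a numbered objective nor a SAP outcome. This is right, and it bounds the importance of the point.

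**Conclusion.** The retention time point does not fit the follow-up described. Linkage at months 6 to 8 requires 18 to 20 months; the spans that the Protocol states or its dates imply are 12 to 18, 15 to 18 and 16 to 19, and about 11 to 19 with the SAP's recruitment period. Within all of these, month-8 linkers can never be assessed. Month-6 linkers are covered in 0% to 33% of cases, and month-3 linkers in 50% to 100%. These shares assume even entry, a 1 June 2015 start and the linkage times shown. Only the nominal, funding-dependent 20 months would cover everyone, and its end date contradicts it.

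Separately, the denominator is unstated, and a linkers-only analysis would lose the protection of randomisation. The documents establish neither the direction nor the size of any bias. The illustrative −8.6 to +2.9 points rest on assumed retention rates and show only that the answer can turn on the denominator. The primary linkage analysis is not affected.

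**What to change.** 1. Reconcile the Patient follow-up, Analysis plan and Duration sections (including the activity chart) with each other and with the SAP's recruitment period, so that there is one follow-up length and one closing date.
2. Define retention at one fixed time from randomisation that every participant reaches before data closure. The 12-month point already in Patient follow-up is a natural choice. With recruitment ending on 31 August 2015, the last participant reaches it on 31 August 2016. With 8 months of recruitment from 1 June 2015, the last reaches it at about the end of January 2017, a month after the stated end, so the cut-off would have to move. A later point such as month 15 would not be reached by all under the one-year minimum or the longer recruitment.
3. Analyse all randomised participants, count those who never linked as not retained, and state in the report that this measure combines linkage and retention.
4. Keep retention from linkage as a descriptive supplement, censored at data closure so that cut-off windows are not scored as failures.
5. Add the outcome and its denominator to the SAP, which currently has neither.

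The cost is wording in both documents, possibly a later data cut-off, and no extra visits. The real loss is horizon: at month 12 a month-6 linker has 12 − 6 = 6 months after linkage and a month-8 linker 12 − 8 = 4.

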Helen Joseph Hospital is approximately 4 km west of Johannesburg's inner-city in the suburb of Auckland Park. As a tertiary clinical site, the hospital provides a number of clinical services including HIV, ANC, PNC, and specialised care services to patients and has a connection with the University of Witwatersrand's Department of Medicine. The area surrounding Helen Joseph Hospital is comprised of mostly black South African middle-income families living in single unit residential dwellings. Helen Joseph Hospital has a catchment population of around 250,000 and an HIV prevalence of approximately 15-20%.

Linkage-to-care rates for all newly diagnosed HIV-positive individuals in both sites are 50-55%. Women have slightly higher linkage rates, at 60%, while men have slightly lower rates, close to 45%. Exact linkage-to-care figures for young adults, those aged between 18 and 25, in this area are unknown. However, previous research has suggested linkage rates for young adults to be 40-45% (Takuva et al 2015). Due to South African laws that protect exploitation of children and the resulting difficulty in including them in research studies, all participants will be 18 years of age or older.

Intervention

This is a multi-site randomised controlled trial in which newly diagnosed HIV-positive patients, fulfilling all inclusion criteria, will be randomised to either receive the intervention (installation of a password-protected laboratory result and HIV-information app on their smartphone) or the standard of care. All patients will be provided with their unique identifier, to present to the clinic, and asked for permission to access their results on the computer, as a means to assess follow up, to phone them and ask them about their experience of HIV care (at the end of the study) and to verify their clinic attendance throughout the study. Participants will be able to provide feedback about the study to the study team by phone or SMS at any time. In return for their time all study participants will receive a R50 study participation allowance, in the form of a mobile phone credit voucher, at the end of their recruitment visit. Participants will be informed that no additional funds will be provided for subsequent appointments.

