6.2 Multicenter study data

This trial is individually randomised but since it is multi-centre it has a clustering aspect which needs to be taken into account in the analysis of outcomes. This clustering is linked to patient population/catchment specificities at the sites as well as facility related characteristics which may differ across the sites. Clustering could theoretically occur within the intervention arm across sites (app training done differently, different information provided the respective field worker despite scripted patient-fieldworker interaction, etc.). However, we believe that the more relevant clustering occurs in both the intervention and control arms, and is an effect of the different sites' patient and service characteristics. We therefore envisage to use a random effects model (sometimes referred to as "random intercept" model - Lee, K and Thompson, S. The use of random effects models to allow for clustering in individually randomised trials. *Clinical Trials* 2005; 2: 163 – 173). This is a realistic model for any clustering across both treatment arms in which it is probable that the clustering is unlikely to have an impact of the treatment effect.

6.3 Exposure variable/s:

6.3.1. A smartphone health application (SmartLink), created by the study team, which provides patients with their CD4 count and viral load, along with explanatory descriptions and HIV/AIDS information.

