6.5 Data transformations

6.5.1. Not expected if sample is normally distributed

6.6 Statistical tests to be conducted

6.6.1. Descriptive analyses

6.6.1.1. Comparison of means

6.6.2. Inference statistical analyses

6.6.2.1. Pearson's exact

6.6.3. Modeling (random effects to allow for multisite design)

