7.3 Tests for homogeneity

Characteristic	Intervention arm	Control arm	Statistical significance (p value)
Mean age (SD)			
Mean education received			
Mean LSM (SD)			
Employment status (n, %)			

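### The primary test of linkage leaves out sex and age, and the plan neither fixes its adjustment variables nor says which analysis is primary

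*Protocol*

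**What the plan says.** **Protocol, Analysis plan.** The primary analysis is "based on a chi-squared test comparing the proportion of individuals between the study arms and within study sites". The plan then adds a logistic model of the same outcome, ranked as secondary, whose covariates are not named. The next paragraph, which begins with the secondary outcomes, ends its account of methods with: "A sensitivity analysis will be conducted using regression analysis to identify and adjust for potential confounders".

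**SAP.** Section 6.2 says of the multi-centre design that "it has a clustering aspect which needs to be taken into account in the analysis of outcomes", and proposes a random intercept for site. Section 6.6 lists a test called Pearson's exact and, separately, random-effects modelling for the multisite design. It does not say which gives the primary result. The results table in 7.4 has room only for counts, percentages and a p value for linkage. No section names sex, age or baseline CD4 as a covariate.

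**What is known about sex and age.** Protocol, Population: "Women have slightly higher linkage rates, at 60%, while men have slightly lower rates, close to 45" per cent. The same paragraph puts young adults at 40–45% from earlier research, but says that local figures are unknown. The Sample Size section repeats that male and younger clients link less often.

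**What is collected.** In protocol Appendix II, the population survey asks every newly diagnosed patient for recruitment site, gender and date of birth.

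**The concern.** When baseline variables are known to be related to the outcome and are collected before randomisation, a model that contains them usually estimates the treatment effect a little more precisely than a crude comparison. The protocol identifies two such variables and makes them its priority subgroups, but the primary test uses neither.

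The second problem is choice. A logistic model with no covariate list, a regression that is to find its own confounders, and an SAP with both a test and a model allow several defensible results for one outcome. The trial is unblinded (SAP 4.3) and the study team does the analysis, so the choice could be made with the results in view. Randomisation makes any baseline imbalance a matter of chance, so covariates are better fixed beforehand on prognostic grounds than identified from the data.

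**Working it through.** **1. Starting point.** The plan gives no figure for adjustment. Its nearest figure is in SAP section 5: about 350 participants suffice for a 20% difference at 80% power and 0.05 significance. With 1:1 allocation (assumed), that is 175 per arm. The formula is n per arm = [1.96√(2p̄q̄) + 0.842√(p₁q₁ + p₂q₂)]² / d². For 50% v 70%:

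- 1.96 × √0.48 = 1.358
- 0.842 × √0.46 = 0.571
- n = (1.929)² / 0.04 = 93 per arm

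From the protocol's range of 50–55%, a 20-point rise needs 89–93 per arm, and 175 per arm gives 97–98% power. If 20% is meant as a relative rise, 175 per arm gives only 47–56%. Adjustment does not change either conclusion.

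**2. Gain from sex.** R² = f(1−f)(p_women − p_men)² / [p(1−p)], where f is the share of men and p the overall rate. The gain in effective sample is 1/(1−R²) − 1. The 60% and 45% come from the protocol; f is assumed.

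| f | p | R² | Gain |
|---|---|---|---|
| 0.3 | 0.555 | 0.21 × 0.0225 / 0.2470 = 0.019 | 2.0% |
| 0.4 | 0.540 | 0.24 × 0.0225 / 0.2484 = 0.022 | 2.2% |
| 0.5 | 0.525 | 0.25 × 0.0225 / 0.2494 = 0.023 | 2.3% |

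**3. Gain from sex plus age.** Assume half are men, age is independent of sex, the age gap is also 15 points, and 30–50% are young.

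- 30% young: R² = (0.005625 + 0.004725) / 0.2494 = 0.042, gain 4.3%
- 50% young: R² = (0.005625 + 0.005625) / 0.2494 = 0.045, gain 4.7%

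**4. Power and type I error by simulation.** 6,000 trials per row, 175 per arm, control linkage 52.5%, half women, 30% aged 18–25, a 15-point sex gap and an assumed 12-point age gap.

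| True difference | Unadjusted | Sex and age fixed in advance | Most favourable of 10 |
|---|---|---|---|
| 0 | 4.9% | 4.9% | 6.8% |
| 10.5 points (20% relative) | 50.8% | 52.7% | – |
| 15 points | 82.9% | 84.2% | – |
| 20 points | 97.6% | 97.8% | – |

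The ten analyses are the crude test, the logistic model with arm only, models with sex, age or both, four models with one irrelevant binary covariate each, and one model with everything. The number and content of this set are assumptions. Simulation error near 5% is about √(0.05 × 0.95 / 6000) = 0.3 points.

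**5. Chance imbalance in sex.** Neither document states stratification. With half women, the standard deviation of the between-arm difference in the share of women is √(2 × 0.25 / 175) = 0.0535. The 95% limit is 1.96 × 0.0535 = 10.5 points, which shifts the crude risk difference by 0.105 × 15 = about 1.6 points. At the protocol's 1000 per arm, the shift would be about 0.7 points.

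**The case against.** A chi-squared primary test with an adjusted secondary analysis is an accepted choice in a randomised trial, and step 4 shows that it holds its type I error. The protocol itself calls the sex differences slight, and an R² of about 2% agrees. The age evidence is weaker still, because local rates are unknown. The sentence about identifying confounders is in a paragraph that opens with secondary outcomes, is labelled a sensitivity analysis and does not recur in the SAP, so it may not concern the primary outcome at all. The 6.8% arises only if a favourable model replaces the named primary test. The SAP also describes randomisation in the past tense, so changing the primary analysis of an open-label trial is itself a late change.

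All of this stands as a limit on the size of the point. It does not remove the point. The secondary logistic model is explicitly for the primary outcome and names no covariates. The SAP sets a test beside a model without ranking them, so the protection that comes from one named primary analysis is weaker than the protocol alone suggests. Lateness is a reason to date the change and to make it before anyone sees outcomes by arm.

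**Conclusion.** The point holds as a modest improvement. The gain is about 2% more effective sample from sex and about 4–5% from sex plus age, or 0 to 2 points of power. The sex figure rests on the protocol's rates and an assumed share of men; the age figure rests on assumed effects. The main benefit is that covariates fixed in advance leave no room to choose among adjusted results.

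Three stronger readings are tempting, but the documents do not support them.

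- **That the analysis ignores site, or is biased or underpowered for lack of adjustment.** Site is covered by the protocol's within-site comparison and the SAP's random intercept. The crude test is valid, and at a 20-point difference its power is already about 97–98%.
- **That the baseline p values in SAP 7.3 will select the covariates.** Nothing says so. That table covers age, education, socio-economic scale and employment, and omits sex.
- **That baseline CD4 is available for everyone and would bring a large gain.** Blood is drawn before recruitment, but the result is not a survey item. It arrives through the NHLS link, and the protocol plans to evaluate the accuracy of the patient identifier. The documents say only qualitatively that patients not eligible for ART are lost more often. A simulated variance cut of 7–13% with CD4 added rests on an assumed effect.

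**What to change.** In the SAP, before outcomes by arm are seen:

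1. Name one primary model for linkage within 8 months, containing arm, site, sex and age group. State how site enters (random intercept or indicators). State the age cut as well, because the SAP gives the young group as 18–25 in 3.2.5 and 18–30 in section 5.
2. Report the standardised risk difference with 95% CI as the headline result, and add it to table 7.4.
3. Keep the unadjusted chi-squared test as a sensitivity analysis.
4. Replace the protocol's step that identifies confounders with this fixed list.
5. Use baseline CD4 only in a supplementary model, with a stated rule for participants without a linked NHLS result, so that no randomised participant is dropped from the primary analysis for want of a CD4 value.

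The cost is a paragraph of SAP text and a few lines of Stata. The one downside is that the conditional odds ratio from the model differs from the crude odds ratio even without imbalance, which is why the standardised risk difference has to be the headline figure.
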